Protocol

JIA (Juvenile Idiopathic Arthritis) Toolbox Feasibility Study

JIA Toolbox Feasibility Study

18/12/2024 Version 2

IRAS number: 336429

The undersigned confirm that the following protocol has been agreed and accepted and that the Chief Investigator agrees to conduct the study in compliance with the approved protocol and will adhere to the principles outlined in the Declaration of Helsinki, the Sponsor's SOPs, and other regulatory requirement.

I agree to ensure that the confidential information contained in this document will not be used for any other purpose other than the evaluation or conduct of the investigation without the prior written consent of the Sponsor

I also confirm that I will make the findings of the study publicly available through publication or other dissemination tools without any unnecessary delay and that an honest accurate and transparent account of the study will be given; and that any discrepancies from the study as planned in this protocol will be explained.

KEY STUDY CONTACTS

Chief Investigator	[name] (Design Researcher at SHU), [contact] [name]
Sponsor	[name], [contact] , [name]
Funder(s)	Medical Research Council (MRC IAA 2023 Call)
Co-Investigator	[name] (Consultant Paediatric Rheumatologist at SCH), [contact] , [name]
Co-Investigator	[name] (Occupational Therapist at SCH), [contact]
Co-Investigator	[name] (Principal Research Fellow at SHU), [contact] , [name]
Co-Investigator	[name] (Researcher and product designer at SHU) [contact]
Advisor	[name] (Director of Juvenile Arthritis Research (JAR) charity)

STUDY SUMMARY

Study Title	JIA Toolbox Feasibility Study
Internal ref. no. (or short title)	JIA Toolbox Feasibility Study
Study Participants	Children with JIA (aged 7-16), their parents and their teachers
Planned Size of Sample (if applicable)	N=25
Planned Study Period	9 months (08.04.24 – 31.07.25)

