Research Question/Aim(s)	
What are the potential impacts of using 'JIA Toolbox' for:
 
 - Children and Young People (CYP) with Juvenile Idiopathic Arthritic (JIA) in terms of improving overall condition management by enabling independence and improved functional ability? - Parents of CYP with JIA in terms of enabling improved condition management? - Healthcare Professionals (HCP's) working in JIA management in terms of improving physio adherence? - and teachers of children with JIA in terms of improving communication around the condition in the classroom?

The Research Team and expertise:

CI: [name] – Design Researcher and Product Designer. Expertise in co-designing technological healthcare solutions and delivering multiple healthcare research projects.

CO-I: [name] – Consultant Paediatric Rheumatologist. Expertise in treating and managing Juvenile Idiopathic Arthritis and delivering healthcare research projects.

CO-I: [name] – Specialist Paediatric Rheumatology Occupational Therapist. Expertise in working with children with JIA on their occupational needs and therefore areas of difficulty that are unmet by current products and delivering healthcare research projects.

CO-I: [name] – Industrial Designer and design researcher. Expertise in designing and prototyping products for industry, including electronic, sensor and textile-based solutions, and delivering a variety of health related research projects.

CO-I: [name] – Principal Research Fellow. Expertise in design and co-design as methods of applied Research and Knowledge Mobilisation in the field of Health and Wellbeing.

The team is highly experienced in:

- Translational research,
- Patient focused research,
- Co-designing solutions,
- Developing products, services and interventions that promote dignity and enhance quality of life,
- And commercialisation of solutions – example ‘head-up’ neck collar (designed, developed and currently on the market) and recently awarded global ‘Made With Patients’ award.

Protocol

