5.0 Study Design

CYP aged 7-16 years with JIA, parents/guardians and HCPs based at Sheffield Children's Hospital (SCH) and/or a part of Juvenile Arthritis Research (JAR) charity will participate throughout this study.

The components of 'JIA Toolbox' are illustrated in Appendix 1. The potential impact of these devices will be assessed by comparing baseline qualitative data about living with JIA, with data collected when the devices are in use. Post-intervention interviews with participants will capture practical usability issues and the potential impact of 'JIA Toolbox' on CYP's wider life, like social impact, to frame possible outcome measures for future evaluation.

The study design is shown in Appendix 2. It will consist of:

WP4

4.1 Recruitment of participants n=25 (CYP aged 7-16) and their parents/guardian from SCH or JAR

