9.0 Statistical Analysis

As this is a qualitative feasibility study, a sample size of 25 is adequate according to Lancaster et al as supported by NIHR when estimating a parameter within a study. This study is testing the effectiveness and viability of 'JIA Toolbox', we are looking at the practicalities of using these prototypes in real contexts and seeking clues as to the potential real-life impacts, by way of specifying further product design refinements and as a way of understanding how a future pilot evaluation study might be practically designed and which outcome measures would be relevant to service users, HCPs and device manufacturers.

At the conclusion of this study, the STOP/GO criteria for continuing onto a larger study will be:

- green light if 50% report a positive change in their condition management,
- amber light requiring potential changes if 30% report a positive change and,
- red light if only 10% report a positive change.

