12.0 Justification of finance and resources

UA time (1 day a week over 18 months (£16,362)): Although PI, UA is the only person who can do this work as it builds on the previous background work of which she has sole and extensive knowledge (specifically relating to the underpinning research, design and development of the prototypes and experience in developing innovations for the JIA population).

Sheffield Hallam University in kind contribution:

- [name] (CO-I): Advising on ethics/research approvals, design aspects, PPIE sessions and general applicable queries as the project develops.
- [name] (CO-I): Consulting on prototype improvements, design and prototype assistance, technical assistance and ongoing advising of related aspects.

Sheffield Children's Hospital in kind contribution:

- [name] (CO-I): Project planning, review of patient information sheets, identification and recruitment of patient participants.
- [name] (CO-I): Review of patient information sheets, identification and recruitment of patient participants.

PPIE sessions with YOUR RHEUM (£1,200) and JAR (Juvenile Arthritis Charity) (£2000): To advise and steer the research at an early stage by CYP with JIA and their families, and input on study design and participant facing materials where appropriate to ensure maximum engagement from the participants involved.

'Thank you' vouchers (£50 per participant (30) = £1500): for participant time to acknowledge participant contribution to encourage engagement.

Technical equipment (£3000): For design and development of the prototypes in line with improvements from proof-of-concept study. Sufficient development and trialling will ensure the systems work well and will be used and engaged with correctly.

Prototype production – Primary manufacturer (£50,000) & heat panel manufacturer (£2,500) : An integral part of the study. The prototypes must be manufactured to a high standard to ensure they work reliably and are robust.

Dissemination and conference fees (£2000): To attend applicable conferences such as Paediatric Rheumatology conference, European rheumatology conference, design4health, European health design conference. This will enable widespread dissemination of the findings (ensuring IP protection is maintained), increasing impact of the research project.

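### The STOP/GO rule gives no light to results between 10% and 30%, which at n=25 leaves 3 to 7 children without a decision

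*Protocol*

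**What the plan says.** Section 9.0 states the criteria for moving to a larger study in three bullets. The first, for going ahead, reads "green light if 50% report a positive change in their condition management". The middle one, for going ahead with modifications, reads "amber light requiring potential changes if 30% report a positive change and", its last word leading on to the final bullet. That final bullet, for stopping, reads "red light if only 10% report a positive change". None carries a lower or upper limit, and no other section completes the rule.

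The same section says that "a sample size of 25 is adequate". Section 5.0 shows who the 25 are: "Recruitment of participants n=25 (CYP aged 7-16) and their parents/guardian from SCH or JAR". The study summary lists the participants more widely, as "Children with JIA (aged 7-16), their parents and their teachers". Its research questions use condition management for the children and again for parents: "Parents of CYP with JIA in terms of enabling improved condition management". The teachers' question is about communication in the classroom.

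The only earlier success rate is in section 3.0: 80% of 10 children in the proof-of-concept study found at least one prototype helpful. No expected rate of positive change is given for the present study.

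**The concern.** A traffic-light rule is useful only if every possible result maps to one light before anyone sees the data. Here the stretch between the red figure and the amber figure maps to none. It is also the stretch where the light matters most, because it separates going on with changes from stopping. If the result fell there, the study team would have to choose the light with the answer in front of them. Sections 3.0 and 13.0 say that the results will support further funding applications, so the choice would not be a neutral one.

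This is not detail that a protocol would normally leave to a statistical analysis plan. The protocol sets the thresholds itself, and following them as written gives no answer over part of the range.

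**Working it through.** **Inputs.** n = 25 children (sections 5.0 and 9.0). Cut-points 50%, 30% and 10% (section 9.0). True rate of positive change, p: not in the protocol, so taken as an assumption and varied from 10% to 50%, with 80% added because of section 3.0.

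**Step 1: cut-points as counts.** 0.50 × 25 = 12.5; 0.30 × 25 = 7.5; 0.10 × 25 = 2.5. On the natural reading:

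- green, at least 50%: 13 to 25
- amber, 30% to under 50%: 8 to 12
- red, at most 10%: 0 to 2
- no light: 3 to 7, that is 3/25 = 12% to 7/25 = 28%

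That is 5 of the 26 possible results.

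**Step 2: probability of each outcome.** With X binomial(25, p), the chance of no decision is P(3 ≤ X ≤ 7) = P(X ≤ 7) − P(X ≤ 2). At p = 0.20 this is 0.8909 − 0.0982 = 0.7927.

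| Assumed true rate | Red (0–2) | No light (3–7) | Amber (8–12) | Green (13–25) |
|---|---|---|---|---|
| 10% | 0.537 | 0.461 | 0.002 | 0.000 |
| 20% | 0.098 | 0.793 | 0.109 | 0.0004 |
| 25% | 0.032 | 0.694 | 0.270 | 0.003 |
| 30% | 0.009 | 0.503 | 0.471 | 0.018 |
| 40% | 0.000 | 0.153 | 0.693 | 0.154 |
| 50% | 0.000 | 0.022 | 0.478 | 0.500 |
| 80% | 0.000 | 0.000 | 0.0004 | 0.9996 |

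**Step 3: does the gap depend on the reading or on n?** If the counts next to the cut-points (3 and 7) are also given a light, 4 to 6 still has none, with probability 0.546 at p = 0.20. With 20 children the gap is 3 to 5 (0.598 at p = 0.20). With 30, the number in the voucher budget of section 12.0 ("Thank you' vouchers (£50 per participant (30) = £1500"), it is 4 to 8 (0.749 at p = 0.20). The gap remains in each case.

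**Step 4: what the missing choice decides.** At p = 0.20, if 3 to 7 is amber, then P(amber) = 0.7927 + 0.1088 = 0.9015 and P(red) = 0.0982. If 3 to 7 is red, then P(red) = 0.0982 + 0.7927 = 0.8909 and P(amber) = 0.1088. The probability of green is the same either way. The unstated choice therefore turns the likely outcome from amber into red.

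**The case against.** The strongest reply is that this is a qualitative feasibility study looking for design lessons, with no hypothesis test, and that any reader takes the bullets as bands. Most of the range can indeed be read that way: on the natural reading 21 of the 26 results get a light. But readers cannot agree on 10% to 30%, because the text supports a weak amber and a red equally.

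A second reply is that the gap may never be reached. The only related figure in the protocol is 80%, and at that rate green is almost certain. This limits the practical exposure, and the 79% should not be quoted alone. But the 80% comes from 10 children and measures whether a prototype was found helpful, not whether condition management changed. A stop rule also has to work when results are poor.

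Three stronger readings are tempting and are not supported:

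- *That no light can ever be reached*, because 12.5, 7.5 and 2.5 are not whole children. This needs exact equality with each percentage, which nobody would apply.
- *That the rule has no unit at all.* Section 5.0 defines the 25 as children and the primary objective in section 4.0 concerns children. Teachers have no condition to manage. What stays open is child or parent, because the parents' research question uses the same term.
- *That the missing denominator is an equal fault.* Whether enrolled or interviewed children count, and how withdrawals are treated, is commonly left to an analysis plan. The protocol gives no dropout figure from which to size the effect. It is worth settling in the same edit, no more.

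**Conclusion.** The point holds in this form: on the natural reading, 3 to 7 of 25 children (12% to 28%) receive no decision under the only progression rule in the protocol. The chance of that is about 46% to 79% if the true rate lies between 10% and 30%, 15% at 40%, 2% at 50% and negligible at 80%. These figures rest on 25 independent reports and on assumed rates; the protocol does not say which rate to expect.

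A reader might infer that everything under 30% is meant to be red, or that everything above 10% is meant to be amber. The text says neither, so this is the sponsor's choice to make and record. It should be fixed, but it does not undermine the study: the consequence is confined to the progression decision, and a short clarification removes it. Contiguous bands do not by themselves define what counts as a positive change; that definition may sit in an analysis plan that is not at hand.

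**What to change.** Replace the three bullets in section 9.0 with contiguous bands in counts of the 25 children. Keep green at 13 or more (50% or more), and state before data collection which option applies below that:

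- **Option (a):** red is 10% or less (0 to 2) and amber is 3 to 12. This keeps the written 10% and moves the start of amber down.
- **Option (b):** amber is 30% to under 50% (8 to 12) and red is 7 or fewer. This keeps the written 30% and moves the top of red up.

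In the same text, name the child as the unit, so that parents' answers to their own condition-management question are not counted in the rule, and fix the denominator. Using all enrolled children, with those who give no report counted as not positive, is a conservative option. Its downside is a less favourable percentage if children withdraw. If fewer than 25 enrol, apply the same percentages to the number enrolled.

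The cost is a few reworded lines, with no change to design, sample size or procedures.

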10.0 Safety Assessment

The study will be monitored and audited in accordance with the Monitoring Standard Operating Procedures of the Directorate of Research & Innovation at Sheffield Children's NHS Foundation Trust. All study related documents will be available on request for monitoring and audits by the Sponsor, the Health Research Authority and the relevant Research Ethics Committee.

Further information is provided in the ***risk assessment form***

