5.8 End of intervention interview (1 hour 1:1 with researcher)

WP6

6.1 Analyse qualitative data with healthcare professionals who are a part of the research team

The end of study is defined as the date of the last interview of the last participant.

As 'JIA Toolbox' consists of therapeutic self-management tools, participants will decide when to use the prototypes during the 3-month intervention period. As such, there should be no added burden to the participants in using these products, as they are designed to assist with condition management rather than hinder. There will be two training sessions, one on how to use the data collection packs (examples shown in appendix 3) and one on how to use the prototypes. This will ensure that the participants are clear on what they should do, minimising any potential risks in interacting with the prototypes. There will be regular weekly check ins to ensure participants are happy with the study and to troubleshoot any issues raised. The 3-month intervention period where the participants are using the devices will take place over August, September and October, giving CYP 1 month to get used to the devices prior to using them in a school context. From the previous proof-of-concept study, it was highlighted that the devices were beneficial in building CYP-teacher relationship near the beginning of the school year. Post-intervention interviews will be conducted at the end of the study to ensure all experiences are equally captured and to give participants the opportunity to highlight anything they feel needs additional clarification.

The study design has had input from YOUR RHEUM which is a group of CYP (11-24) with diagnosed rheumatic conditions, and JAR which is a group of CYP (7-25) with Juvenile Arthritis. Both groups regularly input on CYP rheumatology research. They have a strong track-record in advising on and shaping rheumatology research and represent a 'Gold Standard' approach to PPI involvement. These groups have been involved in shaping the study design and participant facing materials such as the data collection packs to ensure they are appropriate and will be effective. They have also commented on the prototypes themselves, feeling that they fulfill key unmet needs within the JIA population. [name] and [name] are both healthcare professionals who work within

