11.0 Ethical Considerations

1. Risk of unintended distress

Discussion with participants about JIA will be treated sensitively. Interviews may lead to minor distress. To minimise this risk, participants will be informed they do not have to complete any questions or take part in any activities that make them uncomfortable and reminded that they have the right to withdraw at any point and will still receive their thank you voucher. If a participant becomes distressed, the session will be ended sensitively but quickly. Any participant who has shown evidence of distress will be discussed with the study clinicians (DH/CD). The rheumatology team has a clinical psychologist who could be involved if significant distress is felt to have occurred, although it is not anticipated this will be needed.

2. Burden of time

Involvement is optional and participants will receive a 'thank you' voucher. The use of the prototypes is designed to fit around day-to-day activities and to assist rather than be a burden. Difficulty in using the products will be minimised through training and weekly check ins where the project team can trouble shoot any queries.

3. Concern that they can't withdraw

Before each part of the study, participants, parents and guardians will be informed that this is a voluntary research study and they are free to withdraw at any point and it will not affect their future healthcare.

4. Risk of unintentionally worsening symptoms

The prototypes are designed to help improve symptoms and are based upon proven therapies and known and tested technologies that are routinely used in other products on the market, therefore this risk is minimal. Based on the proof-of-concept study, the prototypes were seen as beneficial to symptom manage and did not make any participants symptoms worse.

5. Using the prototypes

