The prototypes are electronic devices and as such could potentially pose a risk to participants. Firstly, in the previous proof-of-concept study there were no safety issues with the devices. Secondly, the devices for this study will be manufactured by CPI, who have an extensive track record of creating safe, efficient and high quality health tech devices. Thirdly, before using the prototypes, a 1 hour training session will be set up with CI [name] to ensure the participants feel confident in using them. The prototypes themselves will use known and tested technologies that are routinely used in other products on the market and therefore the risk of danger is minimal. For prototype 1 which uses a carbon fibre heating element, there will be sensors incorporated into the device which will stop the device if needed to ensure it does not overheat.

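### The protocol sets up no systematic recording of harms, and its STOP/GO rule counts only positive change, so worsening cannot affect the go decision

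*Protocol*

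**What the plan says.** Section 10.0 (Safety Assessment) opens with "The study will be monitored and audited in accordance with the Monitoring Standard Operating Procedures" of the trust's research directorate. It then makes study documents available for audit and refers to a risk assessment form for further information. It names no safety outcome, no event or incident definition, no recording method and no reviewing role.

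Section 11.0 (Ethical Considerations) treats device risk by reassurance and mitigation. Item 4 calls the risk of worsening symptoms minimal, first because the therapies and technologies are established, and then because the earlier study's prototypes "did not make any participants symptoms worse". Item 5 accepts that electronic devices could pose a risk, then cites the earlier study, the manufacturer's record, training and known technology. "For prototype 1 which uses a carbon fibre heating element", it describes sensors that stop the device before it overheats. Item 1 does give interview distress a route, to the study clinicians.

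Section 9.0 (Statistical Analysis) sets the STOP/GO criteria:
- "green light if 50% report a positive change in their condition management"
- "amber light requiring potential changes if 30% report a positive change"
- "red light if only 10% report a positive change"

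Section 5.0 (Study Design) plans baseline, in-use and post-intervention data collection, closing interviews, and weekly contact: "There will be regular weekly check ins to ensure participants are happy with the study" and to deal with problems that participants raise. Section 15.0 (Outcomes) lists symptom experience among the data to be obtained.

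**The concern.** The study puts a heated, vibrating wearable and two other electronic prototypes with children aged 7 to 16 for three months, to be used when they choose. It is meant to judge viability and to decide whether a larger study follows. Harm bears on both questions, yet the section headed Safety Assessment fixes no way of counting it, and all three decision bands look in one direction only.

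Two things are at stake. First, a child who got worse and a child who noticed no difference are treated alike by the rule. Second, if harms come to light only when a family volunteers them, silence cannot be read as absence. The study could then end without a usable numerator or denominator for worsened symptoms, skin effects or device faults. The section 11.0 view that risk is minimal would be carried forward without a planned test, although the prototypes have been refined since the earlier study and will be used for longer by more children (section 3.0).

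**Working it through.** **Inputs**
- Planned sample: 25 children (section 9.0: "a sample size of 25 is adequate").
- Bands: 50%, 30% and 10% reporting positive change (section 9.0), with 50% and 30% read as minimum proportions.
- Earlier study: 10 children (section 3.0), none with worse symptoms (section 11.0, item 4).
- The protocol states no harm rate, harm limit, alpha, power or precision. There is therefore no planned safety figure to reproduce, and the harm rates in step 4 are assumptions shown over a range.

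**1. The plan's thresholds as counts**
- Green: 0.50 × 25 = 12.5, so 13 children.
- Amber: 0.30 × 25 = 7.5, so 8 children.
- Red: 0.10 × 25 = 2.5 children.

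**2. Most children who could worsen under green**
25 − 13 = 12, and 12/25 = 48%. This assumes that all 25 are evaluable and that each child is either positive or worse, not both. If a child can gain from one prototype and be harmed by another, the number harmed could exceed 12.

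**3. What a zero count supports**
With 0 events in n children, the exact upper 95% bound is 1 − 0.025^(1/n) two-sided and 1 − 0.05^(1/n) one-sided.

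| Result | Two-sided | One-sided |
|---|---|---|
| 0 of 10 | 30.8% | 25.9% |
| 0 of 25 | 13.7% | 11.3% |

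The first row holds only if all 10 children used the relevant prototype and were assessed for worsening, which the protocol does not state. The second needs the same of all 25.

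**4. What systematic recording in 25 children could detect**
The chance of at least one affected child is 1 − (1 − p)^25.

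| Assumed true risk p | Chance of at least one in 25 |
|---|---|
| 2% | 39.7% |
| 5% | 72.3% |
| 10% | 92.8% |
| 20% | 99.6% |

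So 25 children are enough to show a common harm, provided that every child is asked.

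**5. Could an existing data source supply the count?**
- Weekly check-ins: stated purpose is satisfaction and troubleshooting; no fixed harm question is stated.
- Baseline against in-use comparison (section 5.0): qualitative, and could show worsening; no count of children worsened is specified.
- Closing interviews (section 5.0): aimed at usability and potential impact.
- Symptom-experience data (section 15.0): could show worsening; not linked to section 9.0.

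All of these could bring harm to light. None is set up to give children with an event out of children exposed, and none enters the STOP/GO rule.

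**The case against.** The strongest reply is that the protocol is not blind to harm. It collects symptom experience before, during and after use, interviews participants, and contacts families weekly. Prototypes are tested by clinical engineering before use, and the qualitative data are analysed with the team's healthcare professionals. A reader might infer from section 10.0 that no harm data are planned at all. The documents do not support that: these sources can show worsening as well as improvement. What stands against the plan is that they do so without a fixed question, a denominator or a link to the decision.

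A reader might also infer that section 10.0 is about audit alone, or that the risk assessment form covers only foreseen hazards. Neither can be claimed. The section refers to the form, and its content is not shown; the same goes for the data collection packs in the appendices. They may contain recording procedures. Even so, section 9.0 would still give harm no role.

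Third, the 10-child record is one of several supports for minimal risk, alongside established technology, manufacturer record, training and the overheat sensors. The 31% bound therefore does not refute the claim. It shows only how little that one support can carry.

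Fourth, the 12 of 25 is subtraction, and a similar remark fits any rule with a single benefit threshold. That is fair: it shows what the rule permits, not what is likely. Nor do the criteria displace ethics or sponsor review.

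Last, tabulating events can be left to a statistical analysis plan, and formal intervals are optional in a study that calls itself qualitative. But what is asked at contacts and who reviews it is study conduct, and the STOP/GO rule is already fixed in the protocol. The absence of an analysis plan does not explain the gap.

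**Conclusion.** The point holds in limited form. As shown, the protocol states no systematic definition, recording or reporting of adverse events or device incidents, and its STOP/GO rule has no harm component. This is more than missing detail, because a stated decision rule disregards worsening.

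As a worst case, green at 13 of 25 is compatible with 12 of 25 (48%) worsening, if all 25 are evaluable and positive and worse exclude each other. It is not a forecast, and nothing in the documents suggests that such harm is expected. The earlier clean record leaves room for a true rate of up to about 31% (two-sided 95%), if all 10 children were exposed and assessed, against about 14% for a systematically recorded 0 of 25. The conclusion on recording is subject to the risk assessment form and appendices, which could not be checked; the conclusion on the STOP/GO rule is not.

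**What to change.** In section 10.0:
- State that each existing weekly check-in asks and logs the same short questions: worse symptoms, skin reaction or burn, device fault or overheat cut-out, and whether use stopped because of it.
- Name the role that reviews the log.
- Report the number of children with any event, by prototype, out of those exposed to it.
- If the risk assessment form or data collection packs already do part of this, say so and cross-refer.

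In section 9.0:
- Report the number of children worsened beside the number improved.
- Require the clinical members of the team to consider that count before green is declared. Whether to set a harm limit, and at what level, is for the sponsor.

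The cost is a few minutes per check-in, a short log and some protocol wording, with no extra visits or participants. The downside is that the go decision may turn out less favourable.
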